4.1.2 Comparative Drug(s)

Tacrolimus, immediate-release, oral; 0.5 mg, 1 mg, 5 mg capsules to be obtained by the transplanting center during a participant’s inpatient stay, and by the patients themselves, thereafter, at retail pharmacies via a study-provided voucher for the study duration of up to 24 months.

IF medically indicated, subjects randomized to the immediate release tacrolimus treatment arm who are unable to tolerate oral administration may be administered tacrolimus via either IV solution, (**Prograf** solution for intravenous use) administered as a 24-hour continuous infusion, or via NGT for no more than seven consecutive days. Dosing via these routes should be discontinued as soon as the subject can tolerate oral administration, and may not exceed a period of seven consecutive days. Additionally, a subject may not receive more than

seven days of combined NGT and IV administration in cases where a subject is switched from one therapy to another. Intravenous tacrolimus will not be provided by the Sponsor.

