5.1.4 Treatment Compliance

Study subjects should be counseled on the need to exhibit 100% compliance with their medication regimen in a manner that reflects a center's own standard of care. As this study is designed to assess the real-world impact of either once-daily Astagraf XL or a twice daily tacrolimus regimen, investigators or their designee should not change how they counsel patients on compliance based on their patient's randomization status or participation in ASTOUND.

Astagraf XL will be monitored by the accounting of unused medication returned by the subject at quarterly visits. Patients receiving immediate-release tacrolimus will be monitored by a third party vendor (via voucher system). Manufacturer, dose, number of pills dispensed, and the date of prescription refills will be captured using a voucher system with a built-in reporting mechanism.

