CV% = $(\sigma/\mu) \times 100$, where σ is standard deviation and μ is mean of the tacrolimus trough levels

Geometric CV% = $\sqrt{\exp(\sigma_{\log}^2)-1} \times 100$, where σ_{\log} is the standard deviation of log-transformed tacrolimus concentration value.

SD = standard deviation

Above three IPV's will also be calculated from dose-adjusted tacrolimus concentration:

Dose-adjusted Tacrolimus Concentration = Tacrolimus Concentration / Tacrolimus Dose of that Day.

Switching of Tacrolimus Manufacturer

The study medication of the BID Immediate-release tacrolimus can be from different manufacturers. A manufacturer switch is counted if the manufacturer(s) of record (based on NDC codes) at one dispensing date are not completely same as those of the previous dispensing.

Compliance

The two common measures of medication adherence using refill data are the medication possession ratio (MPR) and proportion of days covered (PDC). Although the MPR has been used to define medication adherence in kidney transplantation, the PDC seems to be the estimator of choice for CMS and pharmacies. This is due to the fact that the PDC estimator is considered a more conservative measure of refill record-based adherence.

PDC is the percentage of days covered with medication, calculated based on dispensing days from the pharmacy, as shown in the following formula:

$$PDC = \left(\frac{\text{Number of days in period "covered"}}{\text{Number of days in period}} \right) \times 100\%$$

PDC threshold for compliance is typically set at 80% of days covered. This means that someone missing 5 or fewer days' worth of medication in an average month is considered compliant.

Steps to calculate individual PDC based on dispensing data are provided below:

- Step 1: Determine subject's measurement period, defined as the index prescription date until graft loss, death or end of 12-month follow-up period. Index prescription date can be the first fill date after discharge from the hospital for kidney transplantation.
- Step 2: Within the measurement period, count the days the subject was covered (2-daily, immediate release) based on the prescription fill date and days of supply. If prescriptions for the same drug overlap, then adjust the prescription start date to be the day after the previous fill has ended.
- Step 3: Divide the number of covered days found in Step 2 by the number of days found in Step 1. Multiply this number by 100 to obtain the PDC (as a percentage) for each subject.

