- Step 4: Count the number of subjects who had a PDC greater than 80% and then divide by the total number of eligible subject.

MPR is a ratio between number of days of medication supply and number of days in the refill interval. MPR is calculated as:

$$\text{MPR} = \left(\frac{\text{Total number of days of medication supplied}}{\text{Number of days in period}} \right) \times 100\%$$

The number of days in period (e.g., 1 year) is the sum of the number of days from first dispensing (ie., first fill date after discharge from the hospital for kidney transplantation) up to the date of last dispensation plus the number of days' supply obtained at the last dispensation (e.g., 30 days). Any prescription days' supply that spans the 1-year observation period will be truncated at 365 days. MPR threshold for compliance is typically set at 80%.

For this study, the study drug dispense data is only available for the BID Immediate-Release Tacrolimus group. PDC, MPR, and their compliance rates can only be calculated for that treatment group.

Previous and concomitant medication

Previous medication is defined as medications which started and stopped prior to transplant.

Concomitant medication is defined as medications with at least one dose taken between the date of transplant (inclusive) and the date of last dose (inclusive) of study drug.

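### If each capsule strength is its own dispensing record, the PDC overlap rule and the MPR sum count strengths dispensed together as consecutive supply and overstate control-arm refill adherence

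*SAP*

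**What the plan says.** SAP 6.5 (Other Variables, Compliance) sets out PDC in four steps.

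- Step 1 sets the measurement period, "defined as the index prescription date until graft loss, death or end of 12-month follow-up period".
- Step 2 is to "count the days the subject was covered (2-daily, immediate release) based on the prescription fill date and days of supply", and adds: "If prescriptions for the same drug overlap, then adjust the prescription start date to be the day after the previous fill has ended".
- Step 4 classifies patients: "Count the number of subjects who had a PDC greater than 80" percent. The SAP explains the threshold this way: "This means that someone missing 5 or fewer days' worth of medication in an average month is considered compliant".

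For the second measure, "MPR is a ratio between number of days of medication supply and number of days in the refill interval". Its denominator runs from first to last dispensing plus the days' supply of the last dispensing. Supply running past one year is cut at day 365. There is no rule for overlapping or same-date records.

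Protocol 4.1.2 describes the comparator: "Tacrolimus, immediate-release, oral; 0.5 mg, 1 mg, 5 mg capsules to be obtained by the transplanting center". On the data available, Protocol 5.1.4 says: "Manufacturer, dose, number of pills dispensed, and the date of prescription refills will be captured using a voucher system". Days of supply is not among the listed fields. The manufacturer-switch rule in SAP 6.5 works from NDC codes and allows for more than one manufacturer on a single dispensing date.

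Under SAP 6.5 and 7.3.2, PDC and MPR exist only for the immediate-release arm and are summarised descriptively.

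**The concern.** The overlap rule is sound for an early refill of one product, because the surplus is used later. It is not sound for two capsule strengths taken on the same days to make up one dose. Immediate-release tacrolimus in two strengths is, on the plain wording, one drug, and two fills on one date overlap completely. Step 2 then places the second strength after the first, so two concurrent 30-day fills become 60 covered days. MPR adds both supplies in the same way.

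What is at stake is the description of adherence in the control arm. The Protocol background names non-adherence among the main causes of de novo DSA. A reader will therefore look at these rates, and the error would make the arm look more adherent than it was.

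**Working it through.** **Plan's own figure.** PDC = 1 − missed days / days in month. In a 30-day month, 5 missed days gives 25/30 = 83.3%, which passes a cut-off of more than 80%. Six missed days gives 24/30 = 80.0%, which does not. The SAP's equivalence reproduces.

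**Inputs.** The rules and the 80% cut-off are from SAP 6.5, and the three strengths are from Protocol 4.1.2. Four inputs are assumptions:

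- the measurement period is 365 days;
- each fill is 30 days (the SAP's own example for a last fill);
- each strength is a separate record with its own days of supply;
- unless stated otherwise, both strengths are filled on every fill date.

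**Formulas.** True coverage = days with the full dose in hand / 365. PDC as written = days covered after shifting overlapping fills / 365. MPR = sum of days supplied / (first to last dispensing + last supply), cut at day 365. With two 30-day records on the last date, the last supply could be read as 30 or 60 days, so both are shown where they differ.

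**One strength, filled every 60 days (days 0 to 360).** Six full fills plus 5 days: (6 × 30 + 5)/365 = 185/365 = 50.7% on both PDC and MPR.

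**Two strengths:**

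| Fill pattern | True coverage | PDC as written | MPR as written |
|---|---|---|---|
| Every 60 days, last fill day 360 | 185/365 = 50.7% | 365/365 = 100% | 370/365 = 101.4% |
| Every 60 days, last fill day 300 | 180/365 = 49.3% | 360/365 = 98.6% | 360/330 = 109.1% or 360/360 = 100% |
| Every 75 days, last fill day 300 | 150/365 = 41.1% | 300/365 = 82.2% | 300/330 = 90.9% or 300/360 = 83.3% |
| Every 30 days to day 150, then none | 180/365 = 49.3% | 360/365 = 98.6% | 360/180 = 200% or 360/210 = 171.4% |
| Every 30 days throughout | 365/365 = 100% | 365/365 = 100% | 730/365 = 200% |

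The patients in the first four rows hold supply for about half the year or less, and all are classed as compliant.

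**Second strength filled only some of the time.** Take fills every 60 days through day 360. Each of the first six dates on which a second strength is also filled adds 30 covered days; the last date adds none. If a share q of fills includes the second strength, expected PDC is (185 + 180q)/365. This gives 63.0% at q = 0.25, 75.3% at 0.5 and 87.7% at 0.75. Passing 80% needs more than 292 days, so at least four of the six (185 + 120 = 305). At q = 0.5, with fills independent, that has probability (15 + 6 + 1)/64 = 34%.

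**Carrying supply forward only within one product code.** The two strengths then run side by side, and PDC for the first row is 185/365 = 50.7%, the true value. However, supply left over when the manufacturer changes is not carried forward, and this arm may receive any available immediate-release product. MPR still sums both records.

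**After merging strengths filled together.** The first row gives PDC and MPR of 185/365 = 50.7%. The second gives PDC 180/365 = 49.3% and MPR 180/330 = 54.5%. All are below the cut-off.

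**The case against.** The strongest objection is that the error is conditional. It needs separate records per strength, each with its own days of supply, and an overlap rule that pools strengths. The SAP does not say how days of supply is obtained. If it is total mg dispensed over prescribed mg per day, nothing is inflated. This stands, and the conclusion is worded accordingly. Still, the text as written points towards pooling, and no sentence in either document prevents the double count.

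A reader might infer that every reading of the overlap rule gives a wrong number. The documents do not support that. Carrying supply forward within a strength regardless of manufacturer would give the right PDC in these examples. Even the product-code reading is right for a patient with no supply left over at a switch. The SAP states neither.

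The consequence is also small, and this stands in full. SAP 7.3.2 drops the between-group compliance comparisons. The risk-factor list in SAP 7.4.2 does not include compliance, although Protocol 7.4.2 did. No test, model, or primary or secondary endpoint uses PDC or MPR.

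Finally, an MPR of 200% would show up in the reported maximum. That would reveal doubling in patients who refill fully. It would not flag the patient at 101%, and PDC cannot exceed 100%.

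**Conclusion.** The point holds in conditional form and is of low severity. With one record per strength and 30-day fills of both strengths every 60 days, true coverage of about 51% is reported as PDC 100% and MPR about 101%. With the last fill on day 300, about 49% is reported as PDC 98.6% and MPR 100% to 109%. Either way the patient is classed as compliant. The size falls if the second strength is not filled every time.

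The effect is confined to the descriptive control-arm PDC, MPR and compliance rates. Three stronger inferences are not supported:

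- **That the treatment comparison or the DSA/IA results are biased.** Nothing in those analyses uses these measures.
- **That the control arm's compliance rate is badly wrong.** The documents do not say how many patients take two strengths or fill them on the same date.
- **That these are the trial's only adherence data, or that non-adherence is the leading cause of DSA.** Protocol 5.1.4 also provides for counting returned Astagraf XL, although the SAP does not analyse it. The background names non-adherence alongside immunosuppression minimisation or elimination without ranking them.

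**What to change.** In SAP 6.5, for both Step 2 and MPR, define days of supply at regimen level. Strengths dispensed together for one prescribed dose should count as a single concurrent fill. Alternatively, use mg dispensed divided by the prescribed mg per day from the tacrolimus dose records. Carry surplus forward within that regimen across manufacturers, and state that the overlap rule applies to successive refills and not to strengths filled together.

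The cost is a few lines of SAP text and slightly more derivation code before hard lock. The Protocol lists dose, pill count and refill date as captured, and the SAP already uses product codes. Whether the recorded dose means capsule strength or daily dose should be confirmed first. Reported adherence may be lower after the change. It would help to report the number of control patients with two or more strengths on one dispensing date, since that decides how much the change matters.

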7 STATISTICAL METHODOLOGY

7.1 General Considerations

All numeric and categorical efficacy and safety endpoints will be descriptively summarized. For continuous variables, descriptive statistics will include the number of subjects (n), mean,

standard deviation, median, minimum and maximum. Frequencies and percentages will be displayed for categorical data.

Summaries based on the FAS, mFAS, PPS, and BAS (e.g. disposition, baseline and efficacy data) will be presented by planned treatment group, unless specifically stated otherwise. Unless otherwise stated, all analyses will be performed using data pooled across sites. Subject listings of all data from the CRFs as well as any derived variables will be presented.

All statistical comparisons will be made using two sided tests at the $\alpha = 0.05$ significance level unless specifically stated otherwise. All null hypotheses will be of no treatment difference, all alternative hypotheses will be two-sided, unless specifically stated otherwise. P-values will not be adjusted for multiple comparisons. In the event that any analysis set sample size falls below 15 in any treatment group, descriptive statistics will exclusively be reported with no p-values or statistical inferences. In addition, logistic regression analysis and other regression model analysis as planned in the following sections will not be performed for outcome variables that have an event rate of less than 10% (i.e. reported by fewer than 57 subjects).

Unless otherwise specified, all data processing, summarization, and analyses will be performed using SAS[®] Version 9.4 or higher.

A hard database lock will occur prior to the final analysis.

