12.5 Interim Stopping Rules Risk Analysis

The purpose of this appendix is to provide an assessment of favorable scientific outcomes that are possible under the conditions of early termination of the IDTX-MA-3004 study. This analysis explores how it is possible to have a favorable scientific outcome if the study would be terminated early due to the immediate-release tacrolimus arm having a DSA/IA incidence rate less than 0.20.

All analyses in this report are based on SAS version 9.3, a 2-sided test, significance level of 0.05, and power of at least 0.80. Additionally, the conservative distributional assumptions of Fisher's Exact Test are used.

The following figure and table illustrate the difference in statistical significance tests between having a sample of 220 subjects per treatment group (study data from either the one year or two year study design) versus 110 subjects (early termination study data). In this case, the difference between the boundaries of statistical significance for the two possible sample sizes illustrates the risk of the study having insufficient power to statistically detect a difference between the treatment arms due to early termination of the study.

For example, the first line of Table 1 represents a potential scenario where the immediate-release tacrolimus cohort has a 0.19 incidence of DSA/IA. In this scenario, if the sample size per treatment group is N=220, statistical significance will be met with at least 80% power if the Astagraf XL cohort's incidence is 0.093 or less. However, if the size of each treatment group is N=110, statistical significance will be met with at least 80% power if Astagraf XL cohort's incidence of DSA/IA is less than or equal to 0.059. Therefore, in this example scenario, the range between 0.059 and 0.093 for DSA/IA incidence in the Astagraf XL cohort shows the risk of study failure due to early study termination – i.e. had the study not terminated early, the Astagraf XL cohort's DSA/IA incidence would be statistically distinguishable from the immediate-release tacrolimus cohort's incidence; however, with the early termination, there is not sufficient statistical power to detect a difference in DSA/IA incidence between the two cohorts.

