3.1.2 Secondary Objectives

The secondary objectives of the study, as stated in the protocol, have been further clarified and adjusted to more closely address the research questions and in consideration of data availability. They are to:

- Assess the risk factors for each of the following outcomes: Interstitial Fibrosis and Tubular Atrophy (IFTA), IFTA and Inflammation, biopsy-proven acute rejection (BPAR), the four-part traditional composite endpoint, early mycophenolate mofetil (MMF) interruption/discontinuation, and estimated glomerular filtration rate (eGFR) status based on three thresholds 30, 40, and 50 at one year.
- Assess and compare, between treatment groups, the association/correlation of the appearance of DSA with the development of IA on molecular profiling at one year.
- Assess and compare, between treatment groups, the incidence of each of the following, occurring over the course of one year : De novo DSA, C1q-binding DSA, DSA IgG₃ isotype, IA, transplant glomerulopathy (TG), select BANFF histology grades (acute and chronic forms of antibody-mediated rejection (ABMR), acute and chronic active T-cell mediated rejection (TCMR), borderline changes, and IFTA), graft loss, mortality, and BPAR.
- Compare, between treatment groups, the incidence of various thresholds of eGFR (less than 30, 40, 50 mL/min/1.73 m²) at Day 365 visit and a five-point decline from Day 30 to Day 365).
- Summarize the distribution of ordinal categories of antibody strength (weak, moderate, strong) between treatment groups across the 1-year study time course.
- Summarize maximum Mean Fluorescence Intensity (MFI) scores by treatment group across the duration of the study.
- Examine histopathology in cases where biopsies were taken for maintenance (up to fourteen months) between treatment groups. In cases where biopsies were performed for cause, they will be examined separately.
- Summarize tacrolimus manufacturer and the number of switches between immediate-release tacrolimus products by the occurrence of study composite endpoint.
- Summarize tacrolimus manufacturer and the number of switches by the status of renal dysfunction.
- Summarize adverse events (AEs) between treatment groups.

- Summarize the absolute and percent changes in eGFR over the study duration beginning from 30 days post-transplant between groups, and in subjects who develop DSA or IA.

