Following secondary endpoints will be summarized with frequencies and percentages by treatment group. The incidence of events will be analyzed for treatment group differences. Analysis of treatment group differences will be implemented from logistic regression model with the same covariates of primary efficacy analysis.

1. De novo DSA formation
2. IA
3. C1q-binding DSA
4. DSA IgG₃ isotype
5. Persistence of DSA
6. Persistence of IA
7. TG (cg $>$ 0)
8. Microcirculatory Inflammation (g+ptc $>$ 2)

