15. BPAR

16. The four-part traditional composite endpoint

Separate risk factor analyses will be conducted for BID Immediate-release Tacrolimus treatment group only. Manufacturer will be included as additional covariate.

Ordinal assessments of antibody peak strength (weak, moderate, and strong) will be summarized based on the results over the course of one year using frequencies and percentages. Analysis of treatment group difference will be done using Fisher's Exact Test.

The continuous endpoint of Peak MFI score will be summarized with descriptive statistics based on the results over the course of one year by antibody.

Histopathology assessments will be summarized with both descriptive statistics and frequencies and percentages. Raw biopsy scores, including g, t, v, i, cg, ct, ci, cv, ah, ptc, and mm will be summarized as ordinal outcomes. Analysis of treatment group differences will be performed using Fisher's Exact Test. The incidence of binary outcomes including ci, ct, and ptc scores greater than 1 will be summarized with frequencies and percentages. Analysis of treatment group differences will be performed using Fisher's Exact test.

Assessments of association between De novo DSA and IA will be analyzed with logistic regression models using DSA formation as the response and IA as predictor using the same covariates detailed in Section 7.4.1.1.

Mean of eGFR by treatment group will be plotted across visits.

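### SAP 7.1 cancels all regressions for outcomes below 10%, leaving the sixteen between-arm comparisons in SAP 7.4.2 with no planned test

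*SAP*

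**What the plan says.** SAP 3.1.2 sets a secondary objective: "Assess and compare, between treatment groups, the incidence of each of the following, occurring over the course of one year". Its list includes de novo DSA, IA, TG, ABMR, IFTA, graft loss, mortality and BPAR.

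SAP 7.4.2 lists sixteen numbered endpoints, to be reported as frequencies and percentages by arm. It adds "The incidence of events will be analyzed for treatment group differences" and gives one method: "Analysis of treatment group differences will be implemented from logistic regression model with the same covariates of primary efficacy analysis".

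SAP 7.1 sets a general exclusion: the logistic and other regression models planned in the later sections "will not be performed for outcome variables that have an event rate of less than 10% (i.e. reported by fewer than 57 subjects". It does not say what replaces the model. The sentence before it covers a different situation, an analysis set below 15 in any arm. Only for that case does it say "descriptive statistics will exclusively be reported with no p-values or statistical inferences".

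Fisher's exact test does appear in SAP 7.4.2, but not for the sixteen endpoints. For peak antibody strength the text reads "Analysis of treatment group difference will be done using Fisher's Exact Test", and a similar sentence covers the raw biopsy scores and ci, ct and ptc scores above 1.

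**The concern.** The plan commits to comparing incidence between arms, names one method, and then withdraws that method for uncommon outcomes without naming another or saying that those outcomes become descriptive. Nothing in SAP 7.10 fills the gap. The revision history in SAP 8 cites overfitting as the reason for changing the risk-factor plan and chooses descriptive reporting for plasma exchange. Neither entry mentions the sixteen comparisons.

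De novo DSA matters most, because it is half of the primary composite. If its rate is below 10%, the SAP has no planned way to say whether that component differs by arm. Anyone could compute a test from the reported counts, but in an open-label trial it would have been chosen after the frequencies were seen.

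An event floor makes sense for models with many covariates. It is not a reason to drop an unadjusted exact comparison of two proportions.

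**Working it through.** **Inputs.** Two-sided alpha 0.05 (SAP 7.1). Design rates 20% and 10%, 80% power, 220 per arm evaluable, 275 per arm enrolled after 20% dropout (SAP 4, Protocol 7.1). Boundary rates for at least 80% power at N = 220 (table in Protocol 12.5, for which "Additionally, the conservative distributional assumptions of Fisher's Exact Test are used").

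**The plan's own figures.** For 20% versus 10%, the normal-approximation sample size is 199 per arm, or 219 with continuity correction. Exact Fisher power at 220 per arm is 0.811. Then 220 / (1 − 0.20) = 275. The sample size reproduces.

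**Results just below the trigger.** Pooled rate = (x₁ + x₂) / (n₁ + n₂); Fisher two-sided p; Newcombe 95% CI for the difference.

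- 39 vs 15 of 275: pooled 54/550 = 9.8%; p = 0.0008; difference 24/275 = 8.7 points, CI 3.8 to 13.8.
- 29 vs 14 of 220: pooled 43/440 = 9.8%; p = 0.024; difference 15/220 = 6.8 points, CI 1.2 to 12.5.

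Neither would have a planned test or interval.

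**Smallest significant splits at 275 per arm, by total events**

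| Total | Split | Fisher p |
|---|---|---|
| 10 | 9 vs 1 | 0.020 |
| 20 | 15 vs 5 | 0.038 |
| 30 | 21 vs 9 | 0.037 |
| 40 | 27 vs 13 | 0.032 |
| 54 | 35 vs 19 | 0.031 |

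**Protocol 12.5 rows.** Power = the sum over all (x₁, x₂) of Bin(x₁; 220, p₁) × Bin(x₂; 220, p₂) × I(Fisher p ≤ 0.05). Of the 16 rows, 11 have a mean rate below 10%, from (0.14 + 0.057)/2 = 9.85% down to (0.04 + 0.001)/2 = 2.05%. Their recomputed power runs from 0.808 to 0.827.

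**How often the rule would remove a significant result**, reading the trigger as a percentage:

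| True rates | n per arm | P(pooled < 10%) | P(pooled < 10% and Fisher p ≤ 0.05) |
|---|---|---|---|
| 0.12 vs 0.043 | 220 | 0.91 | 0.73 |
| 0.12 vs 0.043 | 275 | 0.93 | 0.83 |
| 0.14 vs 0.057 | 220 | 0.52 | 0.40 |
| 0.14 vs 0.057 | 275 | 0.53 | 0.45 |

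These rates come from a table about the composite. Applying them to a secondary endpoint is an assumption.

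**The two forms of the trigger.** Fewer than 57 events means the same as below 10% only if 10% of N, rounded up, is 57, that is for N = 561 to 570. At N = 550 the two forms disagree for 55 and 56 events. At N = 440 they disagree for 44 to 56 events.

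**The case against.** The strongest reply is that descriptive reporting was intended. SAP 7.1 opens by saying that all endpoints are summarised descriptively, the regression rule follows directly on a descriptive-only rule, and 7.4.2 commits to frequencies first. That reading is plausible, but the SAP does not state it. Where the authors bar inference in 7.1 they say so, and only for very small analysis sets. Even if it was the intention, it conflicts with the comparison promised in 3.1.2 and 7.4.2.

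Several limits on the consequences do stand:

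- **Partial coverage.** The Fisher tests on raw biopsy scores reach the component scores of items 7 to 10 (TG, microcirculatory inflammation, IFTA, IFTA with inflammation). The listed endpoints themselves are not tested, except that TG is largely reflected in cg.
- **Power.** The Protocol 12.5 rates were solved to give 80% power, and the 11 rows assume reductions of 59% to 97.5%. For a halving, as in the design assumption, exact Fisher power at 220 per arm is 0.54 (12% vs 6%), 0.45 (10% vs 5%), 0.35 (8% vs 4%), 0.25 (6% vs 3%) and 0.15 (4% vs 2%). At 275 per arm it is 0.65, 0.55, 0.44, 0.33 and 0.20. Many sparse comparisons would be inconclusive, but an interval would show that and counts alone do not.
- **Setting.** The trial calls itself exploratory and secondary p-values are unadjusted. DSA and IA are measured centrally, DSA adjudicators are blinded to allocation, and the central pathologist is blinded to clinical results. This lessens bias in measurement. It does not address choosing the analysis after seeing the counts.
- **The figure 57.** Actual enrolment is not given, so 57 may be 10% of one real analysis set. N = 440 is a low case, because dropout alone does not remove a subject from the mFAS.

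**Conclusion.** The concern holds. Followed as written, the SAP leaves a stated secondary objective without a planned test or interval for any of the sixteen endpoints below 10%. The loss can be material: differences of 7 to 9 points with Fisher p-values of 0.024 and 0.0008 would go untested. If a secondary endpoint had true rates of 0.12 and 0.043, about 73% (220 per arm) to 83% (275 per arm) of trials would give a significant exact test that the plan does not provide for.

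How many endpoints are affected cannot be determined, because the documents give no expected rates for them. The primary endpoint is not at issue: SAP 7.4.1.1 separately provides its difference in proportions with a 95% CI.

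The mismatch between 10% and 57 is a secondary point. The two may agree for one analysis set, but if the rule applies to each set, one count cannot be 10% of the mFAS, PPS and BAS when these differ in size. This should be fixed, but it does not threaten the primary analysis.

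**What to change.** Add to SAP 7.4.2 that, for any of the sixteen endpoints below the trigger, the between-arm comparison will be Fisher's exact test with a 95% CI for the risk difference. Keep the cancellation in SAP 7.1 for the regression models themselves, chiefly the risk-factor models with many covariates. State the trigger once, either as a percentage of each model's own analysis set or as a minimum number of events.

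This is a short SAP edit using standard code and no new data. The price is a few more unadjusted p-values and some wide intervals for sparse endpoints.
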